4. ASSESSMENT OF SAFETY PARAMETERS

4.1. Safety Endpoints

The assessment of the safety of treatment was carried out based on registration of adverse events by analyzing complaints and subjective symptoms, comparative analysis of clinically significant changes in laboratory data, as well as the severity of these changes, using the CTCAE scale version 4.03 from 2010.

The study will evaluate the following safety variables:

- frequency of AE/SAE registration in treatment groups (in general and by organ systems);
- changes in vital signs (heart rate, blood pressure, body temperature, respiration rate and SpO₂) during the study (by visits and groups).

4.2. Registration, analysis, and evaluation of safety parameters

Adverse events were recorded from the moment of signing the informed consent until the end of the study. The safety analysis of the drug will consider the data of physical examination, diaries of participants, laboratory tests or other assessments. The study will analyze the frequency of occurrence and the nature of AE and SAE. The safety assessment was carried out throughout the study.

Adverse event (AE)

Adverse event (AE) – any adverse change in the state of health of the patient or the subject of a clinical trial to whom the drug (study) product was prescribed, regardless of the causal relationship with its use. AE may represent any adverse and unintended change (including deviation of the laboratory indicator from the norm), symptom or disease, the time of occurrence of which does not exclude a causal relationship with the use of drug product, regardless of the presence or absence of a relationship with the use of drug product¹.

Symptoms of acute respiratory infection: fever, manifestations of general infectious intoxication, signs of respiratory damage are not considered as adverse event, however, they are recorded during the study and analyzed as data for evaluating effectiveness.

Adverse reaction (AR)

Adverse reaction (AR) – an unintentional adverse reaction of the body associated with the use of a drug and suggesting the presence, at least, of a possible relationship with the use of a suspected medicinal product.

Determination of a serious adverse event (SAE)

Serious adverse event (SAE) – AE that leads to death², poses a threat to life³, requires hospitalization of the patient or its prolongation⁴, leads to persistent or severe uncapacity or disability, to congenital anomalies or malformations⁵, requires medical intervention to prevent the development of these conditions.

¹ Due to statistical necessity, adverse events are recorded both in the study group and in the control group. Evaluation and registration of adverse events begins from the moment of signing the informed consent form.

² Death is an outcome, not the SAE itself, so such a name should not appear as a name. If a case of death for an unknown reason is identified, researcher should make every effort to identify its suspected causes. SAE in such cases can be referred to as "Death by unexplained cause" only in cases where the causes of death are not known and cannot be clarified. In case of a fatal outcome due to COVID-19, the information is recorded in the primary medical documentation of the study participant without registration of the SAE.

³ The term "Life threatening" in this context means that the volunteer participating in the study was at immediate risk of death during the occurrence of adverse event. This term does not apply to cases where adverse event could hypothetically cause the death of a participant if it were more intense in severity or longer in duration.

Unexpected adverse event (Unexpected AE) – adverse event, the nature, severity, or outcome of which does not correspond to the information in the current instructions for the medical use of the drug or in Clinical Investigation Brochure for an unapproved drug.

All **unexpected serious adverse events (unexpected SAE)** those recognized by the researcher as related to the drug are classified as **unexpected serious adverse drug reactions (unexpected SAE)**. Serious adverse drug reaction report form is presented in Appendix 3.

Intensity of adverse event

All AE are registered in the primary medical documentation of the participant based on physical examination, survey and diary records. The following information must be recorded in the primary medical documentation (outpatient card) for each AE:

- severity (mild, moderate, severe);
- nature of adverse event;
- relationship with study drug;
- duration (date of occurrence and end date), preferably with an indication of the time interval (hours) from the moment of administration of the study drug;
- whether adverse event is serious.

The severity is assessed using the CTCAE scale version 4.03 from 2010. The CCAE scale contains a list of the most frequent AE recorded in clinical study, in tabular format, indicating criteria of various degrees of severity (from 1 to 5, where 5 is death because of AE). For AE that are not in the tabulated list, the severity is determined in accordance with the textual description of the degrees of severity.

The terms "serious" and "severe" are not synonymous. The term "severe" is often used to describe the intensity (severity) of a particular event (for example, anemia of severe, moderate, or mild severity); however, the event itself may be clinically insignificant (for example, severe headache).

The concept of "severe" is not equivalent to the concept of "serious". The criteria of the latter are the outcome of the event or the measures, which are usually associated with the elimination of life threatening or severe disorders of vital activity. The criterion of seriousness, and not the severity of adverse event, should be guided when determining the need for expedited safety report of LLC "NPP "Pharmaclon" and authorized agencies.

Criteria for assessing the association of adverse event with the intake of study drug

Methods for assessing the degree of causal relationship are based on the following criteria:

- the presence of a reliable temporary association of the AE with the use of the study drug (AE are registered after the start of the use of the study drug before the completion of participation in the study);
- presence of a direct temporary connection of the AE with specific administration of the drug (for example, the development of AE during instillation);
- possibility of explaining the development of AE by the pharmacological effect of the drug;
- availability of information about such AE as a possible side effect in Clinical Investigation Brochure/guidelines for medical use;
- description of similar cases in the literature;

⁴ Hospitalization for optional or pre-planned treatment of concomitant diseases that the participant had prior to inclusion in the study, the course of which did not worsen during participation in the study, is not considered to SAE, as well as being in a hospital for less than 24 hours or hospitalization for social reasons.

⁵ Pregnancy cases in the participants of the clinical study are not subject to registration as AE, except in cases when the child has formed a congenital anomaly or malformation (the case is registered with SAE).

- presence of additional specific data indicating the association of AE with the drug (for example, the presence of specific antibodies, positive result of allergological tests);
- positive test with the withdrawal of the study drug (AE was resolved or its severity decreased after the drug was discontinued);
- positive test with repeated administration of study drug (AE reappeared or its severity worsened with repeated administration of the drug after withdrawal);
- presence of other reasons for the development of this AE (manifestations of the underlying disease, concomitant diseases and conditions, concomitant therapy, food, lifestyle, etc.).

The association of adverse events with the study drug will be evaluated based on the following principles in accordance with the WHO classification:

- **reliable** – clinical manifestations, including violations of laboratory parameters that occur during the period of taking drugs and which cannot be explained by the presence of existing diseases and the influence of other factors and chemical compounds. Manifestations of an adverse reaction regress after the drug is discontinued and occur when it is re-prescribed;
- **probable** – clinical manifestations, including changes in laboratory parameters associated with the instillation of the drug, which are unlikely to be related to concomitant diseases or other factors and which regress with the withdrawal of the drug. The response to the rechallenge is unknown;
- **possible** – clinical manifestations, including changes in laboratory parameters associated with the use of the drug, but which can be explained by the presence of concomitant diseases or taking other drugs and chemical compounds. Information about the reaction to drug withdrawal is unclear;
- **questionable** – clinical manifestations, including changes in laboratory parameters, which occur in the absence of a clear temporal connection with taking medication; there are other factors (drugs, diseases, chemicals) that may be the cause of their occurrence;
- **conditional** – clinical manifestations, including violations of laboratory parameters attributed to "adverse reactions" that need additional data (for an accurate assessment) or these obtained data are currently being analyzed;
- **unclassifiable** – reports of a suspected adverse reaction cannot be evaluated because there is not enough information or it is contradictory.
- **unrelated** – clinical manifestations are not associated with the use of the drug.

In order to determine the unambiguous connection of AE with the intake of the study drug, an approach will be used in which the presence of at least a possible relationship is assumed.

5. STATISTICAL DATA PROCESSING

5.1. Statistical methods of analysis

To create conditions for an independent evaluation of the results obtained, statistical data processing at the end of the study will be carried out by employees who are not related to the management of the subjects participating in the study. The primary data base was created in Excel when processing registration cards received from the clinical center. Data processing will be performed in the software environment of the R package (R: A language and environment for statistical computing. R Core Team. R Foundation for Statistical Computing, Vienna, Austria)⁶ version 4.1.0 using "A Guidance Document for the Use of R in Regulated Clinical Trial Environments"⁷.

Descriptive statistics are presented for all baseline indicators collected during the study for all subjects included in the study (safety-population). The distribution of subjects, demographic and initial characteristics are presented using descriptive statistics methods.

For numerical indicators, such as demographic and anthropometric data (body weight, age, height, BMI), as well as numerical performance parameters will be calculated:

- Number of missing values (N);
- Minimum value (Min);
- Maximum value (Max);
- Arithmetic Mean (M);
- Standard Deviation (SD);
- Median (Me).

For qualitative variables (frequency of AE/SAE development, for example), absolute number in the n/N format will be given, as well as the percentage (%).

Verification of the normality of the distribution will be carried out by one of the generally accepted methods (visualization of data in a dot diagram in combination with the calculation of the Kolmogorov-Smirnov test, as well as the test for asymmetry and kurtosis).

In the case of a normal distribution, an intergroup comparison of quantitative characteristics will be carried out using the t-test (or the Mann-Whitney test otherwise). For categorical data, the χ^2 -criterion or the exact Fisher test will be applied if the expected frequency in any of the cells is less than 5.

If statistically significant differences between the groups are found, the magnitude of the differences between the study groups will be estimated using confidence intervals. Significance levels and confidence intervals will be calculated as two-sided, and the statistical significance of the differences is by default two-sided and refers to a significance level of 0.05.

Correction for multiple comparisons is not required.

Analysis of the source data

Demographic characteristics, baseline, and follow-up characteristics such as anamnesis, comorbidities and medications used will be described by treatment groups for the ITT population and then safety, if they differ.

⁶ URL <https://www.R-project.org/>

⁷ <https://www.r-project.org/doc/R-FDA.pdf>

Primary Endpoint Analysis

The main parameter of the effectiveness of the preventive use of Ingaron® is the proportion of patients with acute respiratory viral infections, including COVID-19, at the end of the period of preventive administration of the drug (measurement time: 28 days).

In accordance with the purpose and objectives of the study, the null and alternative hypotheses are formulated as follows:

- Null hypothesis (H_0) consists in the assumption that the prophylactic administration of Ingaron will not lead to a change in the incidence of acute respiratory viral infections, including COVID-19, among adult volunteers;
- Alternative hypothesis (H_a) is that in the study group, the proportion of ARVI cases, including COVID-19, will differ from the control group.

$$H_0: \mu_1 = \mu_2$$

$$H_a: \mu_1 \neq \mu_2,$$

where μ is the fraction of the main variable for the corresponding group.

To test these hypotheses, the method of a two-way variant of the Fisher's exact test (with expected frequencies less than 5) or the Pearson's chi-squared test (χ^2) (with the Yates correction for expected frequencies more than 5, but less than 10) will be used.

In all cases, the significance level (α is the probability of an error of the first kind) 0.05 will be used.

The analysis of the primary efficiency parameter will be carried out on the ITT population (main analysis), as well as – additionally – on the PP population (additional analysis).

Data on the case of ARVI (COVID-19) is collected during the entire study by filling out a form on the registration of a case of ARVI.

Secondary Endpoint analysis

The following secondary efficacy parameters in this study are quantitative indicators that will be compared between treatment groups:

- proportion of patients with confirmed COVID-19 at the end of the period of preventive administration of the drug (measurement period: 28 days);
- proportion of patients with acute respiratory viral infections, including COVID-19, at the end of the observation period (change period: 2 months);
- percentage of patients with confirmed COVID-19 at the end of the follow-up period (change period: 2 months);
- Frequency of development of complicated course of ARVI.

The proportion of patients will be presented as a frequency, a percentage in % indicating a bilateral 95% CI, measured according to the data recorded at the time of the corresponding measurement period. For a comparative analysis of the proportions between the groups, method of a two-sided version of the Fisher's exact test (with expected frequencies less than 5) or the Pearson chi-squared test ($2\chi^2$) (with the Yates correction for expected frequencies more than 5, but less than 10) will be used.

The analysis of secondary performance parameters will be carried out both on the ITT population (main analysis) and on the PP population (additional analysis).

Analysis of safety parameters

The study plans to analyze the following security variables:

- frequency of AE/SAE registration in treatment groups (in general and by organ systems);
- changes in vital signs (heart rate, blood pressure, body temperature, respiration rate and SpO₂) during the study (by visits and groups).

For categorical safety indicators in each group and for each visit, according to the survey scheme of participants, frequency, percentage in% and bilateral 95% CI will be calculated. Comparing groups by categorical indicators with the number of categories less than 5, Fisher's exact test will be used, otherwise Pearson chi-squared test (χ^2) will be used (with Yates correction for expected frequencies of more than 5, but less than 10).

The results of measuring vital signs (assessment of heart rate, respiration rate, blood pressure, body temperature and SpO₂) will be presented by treatment groups using descriptive statistics.

The analysis of safety parameters will be carried out on the safety population.

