The primary criterion of effectiveness is the proportion of patients with acute respiratory viral infections, including COVID-19, at the end of the period of preventive administration of the drug (measurement time: 28 days). Secondary efficacy criteria: proportion of patients with confirmed COVID-19 at the end of the period of preventive administration of the drug (measurement period: 28 days); proportion of patients with acute respiratory viral infections, including COVID-19, at the end of the follow-up period (change period: 2 months); proportion of patients with confirmed COVID-19 at the end of the follow-up period (period of change: 2 months); and the frequency of development of complicated course of ARVI.

The literature analysis conducted on similar studies of the effectiveness and safety of the use of interferon-gamma shows that the incidence of ARVI can be observed in 2% of cases in the main group of patients taking interferon gamma, as well as in 14% of the control group taking alternative methods of protection and representing medical workers working in the "red zone" and those at high risk through frequent and prolonged contact with infected patients ($p < 0.05$).

Provided incidence in the control group is from 1 to 5% (taking into account the assumption that the incidence in the control group will be approximately equal to the average incidence of the general population) [29], and incidence in the study group will be at least 3% lower (which can already be considered a minimally clinically significant decrease in incidence in the absence of preventive measures with proven effectiveness, which could be taken as a standard), minimum sample size should be 630 patients (taking into account 10% of early retirement). Such a sample size will also make it possible to establish a decrease in incidence by 4% or more when incidence is set at up to 8% in the control group and a decrease in incidence by 6% or more when the incidence is set at up to 18% in the control group (Table 1 – Dependence of the sample size on various parameters).

The calculation of the required sample size was performed using a formula for calculating the sample size for a qualitative sign [30]:

$$n = \frac{P_1 * Q_1 * t^2 + P_2 * Q_2 * t^2}{(P_1 - P_2)^2}$$

Note to the formula:

P – proportion of cases in which the study sign occurs,

Q – proportion of cases in which the study sign does not occur,

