- ❖ All participants included in the study (FAS, Full Analysis Set). This population will be used to describe basic characteristics, including demographic and anthropometric indicators, data on concomitant diseases, and will also be used as the main population to assess performance parameters. In this case, the participant's group will be determined by the "intention to treat" (ITT Analysis).
- ❖ Auxiliary analysis of effectiveness parameters is planned for all subjects who completed the study without significant deviations from the study protocol (PP, Per Protocol).

Methods of descriptive statistics

For numerical indicators, such as demographic and anthropometric data (body weight, age, height, BMI), as well as numerical performance parameters will be calculated:

- Number of missing values (N);
- Minimum value (Min);
- Maximum value (Max);
- Arithmetic Mean (M);
- Standard Deviation (SD);
- 95 % confidence interval (CI) for the mean;

- Median (Me).

For qualitative variables (frequency of AE/SAE development, for example), absolute number in the n/N format will be given, as well as the percentage (%).

Analysis of basic characteristics

The distribution of subjects, demographic and baseline characteristics will be presented using descriptive statistics methods for all subjects included in the study (FAS-population). An intergroup comparison of the basic quantitative characteristics will be carried out using the t-test (or the Mann-Whitney test), depending on the type of data distribution. For categorical data, the χ^2 -criterion or Fisher's exact test will be applied if the expected frequency in any of the cells is less than 5.

Standard methods available in the XLSTAT 2020.3 program will be used for data analysis.

When analyzing numerical data, preliminary testing of variables for the normality of the distribution will be carried out using Shapiro-Wilk's test, as well as a test for asymmetry and kurtosis with an indication of the p value when testing the null hypothesis of the normal distribution of the variable. In the case of a normal distribution, an intra-group comparison of parameter changes is carried out using a paired t-test. For a comparative evaluation, the χ^2 -criterion or the exact Fisher test will be used if the expected frequency in any of the cells is less than 5.

Significance level

A significance level of 0.05 will be used in all tests. Correction for the multiplicity of comparison is not introduced.

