Thus, the safety population will be used to present demographic data about participants, as well as for safety assessment. ITT will be considered the main sample for comparative analysis of performance parameters. The PP population will include only participants who completed the study without critical deviations from the protocol and will be formed as an additional sample to evaluate the effectiveness parameters in order to analyze the sensitivity of the results obtained in the ITT population. The modified populations will be used to perform sensitivity analysis when evaluating the primary endpoint.

The number of participants who must complete the study in accordance with the protocol is 286 in each group, or a total of 572 participants.

The number of randomized participants is 315 in each group or total of 630 participants.

The number of screened participants is up to 642.

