6. TABLE PATTERNS

Table1. Distribution of subjects

Distribution of subjects	Group I (proportion, %)	Group II (proportion, %)
Included in the study (screened)	n/N (%)	
Of these:		
Excluded at the screening stage:	n/N (%)	
Randomized	n/N (%)	n/N (%)
Prematurely excluded, out of them:	n/N (%)	n/N (%)
Existence of exclusion criterion #X (description)	n/N (%)	n/N (%)
Population safety	n/N (%)	n/N (%)
ITT population	n/N (%)	n/N (%)
Population PP	n/N (%)	n/N (%)

Table2. Demographic and anthropometric characteristics of subjects at the time of inclusion (safety population)

Group	Parameter	Age (years)	Weight (kg)	Height (cm)	Smoking index (p/y)	Frequency of acute respiratory infections (amount/g)
GROUP I	n					
	M					
	CO					
	min.					
	max.					
	Me					
GROUP II	n					
	M					
	CO					
	min.					
	max.					
	Me					
p (between groups)						

Table3. Distribution of subjects by gender (safety population)

Gender	GROUP I	GROUP II
Male	n/N (%)	n/N (%)
Female	n/N (%)	n/N (%)
p (between groups)		

Table4. Distribution of subjects by race (safety population)

Race	GROUP I	GROUP II
Caucasian	n/N (%)	n/N (%)
Mongoloid	n/N (%)	n/N (%)
Negroid	n/N (%)	n/N (%)
p (between groups)		

Table5. Medical history (safety population)

Parameter	Value	Group I (N =)	Group II (N =)
Diagnosis (chronic disease)	...	n/N (%)	n/N (%)
Diagnosis (according to anamnesis)	...	n/N (%)	n/N (%)
p (between groups)			

Table 6. Methods of nonspecific prevention (safety population)

Type	Frequency	GROUP I	GROUP II
Total subjects		N =	N =
Masks	Yes	n/N (%)	n/N (%)
	No	n/N (%)	n/N (%)
	Sometimes	n/N (%)	n/N (%)
Respirator	Yes	n/N (%)	n/N (%)
	No	n/N (%)	n/N (%)
	Sometimes	n/N (%)	n/N (%)
Gloves	Yes	n/N (%)	n/N (%)
	No	n/N (%)	n/N (%)
	Sometimes	n/N (%)	n/N (%)
Glasses	Yes	n/N (%)	n/N (%)
	No	n/N (%)	n/N (%)
	Sometimes	n/N (%)	n/N (%)
Surgical overalls	Yes	n/N (%)	n/N (%)
	No	n/N (%)	n/N (%)
	Sometimes	n/N (%)	n/N (%)
p (between groups)			

Table 7. Drug allergy (safety population)

	GROUP I	GROUP II
Total subjects	N =	N =
No	n/N (%)	n/N (%)
Yes	n/N (%)	n/N (%)
p (between groups)		

Table 8. Results of the assessment of the incidence rate at the end of the prevention period (ITT/PP/ITT_NV/PP_NV/ITT_NV_BE/PP_NV_BE population)

	GROUP I	GROUP II
Total subjects	N =	N =
ARVI	n/N (%)	n/N (%)
Not sick	n/N (%)	n/N (%)
p (between groups)		

Table 9. Results of the assessment of the incidence of COVID-19 at the end of the prevention period (ITT population, PP)

	GROUP I	GROUP II
Total subjects	N =	N =

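### The SAP plans a confidence interval for the between-group difference only after a significant test, so a non-significant primary result has no planned interval to set against the 3-point minimum effect

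*SAP*

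**What the plan says.** The general methods text in SAP 5.1 states: "If statistically significant differences between the groups are found, the magnitude of the differences between the study groups will be estimated using confidence intervals". It adds: "Significance levels and confidence intervals will be calculated as two-sided". No effect scale (difference or ratio) and no interval method is named.

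The other places where an interval might be expected do not supply one:

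- **SAP 5.1, Primary Endpoint Analysis.** It gives hypotheses, the test rule ("To test these hypotheses, the method of a two-way variant of the Fisher's exact test", or chi-squared at larger expected counts), alpha and populations. It gives no effect measure.
- **SAP section 6, Table 8** ("Results of the assessment of the incidence rate at the end of the prevention period"). The shell has n/N (%) per group and a p-value.
- **SAP 5.1, Secondary Endpoint analysis.** "The proportion of patients will be presented as a frequency, a percentage in % indicating a bilateral 95% CI" describes each group's proportion for the secondary endpoints. The safety subsection has a similar per-group interval.
- **Protocol, Methods of descriptive statistics.** The only interval listed is a 95% "confidence interval (CI) for the mean" of numerical variables.

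The benchmark comes from the Protocol, Number of participants. For a control incidence of 1 to 5%, a reduction of at least 3 points "can already be considered a minimally clinically significant decrease in incidence". SAP 5.5 sets the main analysis set: "ITT will be considered the main sample for comparative analysis of performance parameters".

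**The concern.** A non-significant test can mean two different things: a reduction worth having has been ruled out, or the trial was too imprecise to tell. The Protocol has defined a reduction worth having, so the question can be answered, but only with an interval for the difference. The plan drops that interval in exactly this case.

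The condition also distorts the estimates that do appear. If the size of the effect is reported only after significance, the reported values are the larger ones by selection.

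If an interval is added after a null result, its scale and method will be chosen with the data in view, in an open-label study whose report the sponsor approves (Protocol, Research Report).

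**Working it through.** **Inputs.** 315 randomised and 286 completing per group (SAP 5.2); two-sided alpha 0.05 (SAP 5.1); 3-point reduction with control incidence up to 5%, so 5% vs 2% at the upper end (Protocol, Number of participants). Event counts and other true rates below are assumptions.

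**1. The plan's own sample size.** The printed formula with t = 1.96 gives n = (0.05×0.95 + 0.02×0.98) × 1.96² / 0.03² = 0.0671 × 3.8416 / 0.0009 = 286.4, and 286.4 × 1.10 = 315. This reproduces the plan's figures and confirms that the 3 points are absolute.

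**2. Expected precision.** The Wald half-width at 5% vs 2% with 315 per arm is 1.96 × √(0.0671/315) = 0.0286, about 2.9 points. The interval is about as wide on each side as the effect of interest, so where it falls matters.

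**3. What a non-significant p-value hides.** The Newcombe interval is built from the Wilson limits (l, u) of each arm. With d = control proportion minus Ingaron proportion:

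- lower limit = d − √[(p_C − l_C)² + (u_I − p_I)²]
- upper limit = d + √[(u_C − p_C)² + (p_I − l_I)²]

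Wilson limits at n = 315, in %: 16 cases, 5.079 (3.150 to 8.091); 8 cases, 2.540 (1.292 to 4.931); 20 cases, 6.349 (4.147 to 9.603).

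For 16 vs 8, the upper limit is 2.540 + √(3.012² + 1.248²) = 5.80 and the lower limit is 2.540 − √(1.929² + 2.391²) = −0.53. For 16 vs 20, the upper limit is −1.270 + √(3.012² + 2.202²) = 2.46.

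| Cases, control vs Ingaron | p (SAP rule) | Reduction, points | Newcombe 95% CI | 3 points excluded? |
|---|---|---|---|---|
| 16 vs 8 | 0.096 | 2.5 | −0.5 to 5.8 | no |
| 16 vs 16 | 1.0 | 0 | −3.6 to 3.6 | no |
| 16 vs 20 | 0.49 | −1.3 | −5.1 to 2.5 | yes |
| 9 vs 9 | 1.0 | 0 | −2.8 to 2.8 | yes |
| 5 vs 5 | 1.0 | 0 | −2.3 to 2.3 | yes |

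All five would appear in Table 8 as counts and a non-significant p. The three rows with p = 1.0 do not even agree on whether 3 points is excluded.

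**4. How often the plan leaves no interval.** Exact enumeration of two independent binomials used the SAP rule: Fisher if the smallest expected count is below 5, Yates from 5 to below 10, otherwise Pearson; significant if p ≤ 0.05.

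| Assumed true rates, control vs Ingaron | P(non-significant), 315/arm | 286/arm |
|---|---|---|
| 5% vs 2% | 48% | 54% |
| 4% vs 1% | 38% | 44% |
| 3% vs 0% | 9% | 14% |
| 8% vs 4% | 42% | 47% |
| 18% vs 12% | 44% | 48% |
| 14% vs 2% | about 0% | about 0% |
| 5% vs 5% | 95% | 95% |
| 2% vs 2% | 98% | 98% |

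At the stated 80% power the figure would be 20%.

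**5. What the interval would add.** Among non-significant results at 315 per arm, the Newcombe interval excludes a 3-point reduction in 0.0231/0.4834 = 5% of trials if the truth is 5% vs 2%, and in 0.3531/0.9494 = 37% if it is 5% in both arms. At 2% in both arms it is 0.6766/0.9758 = 69%, but a fall of 3 points from 2% is impossible, so that figure mostly reflects low incidence.

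**6. Selection when only significant results are sized.** With true rates of 5% and 2% and 315 per arm, the observed reduction averages 4.1 points in significant trials and 1.8 in the rest, against a true 3.0. As a check, 0.517 × 4.11 + 0.483 × 1.81 = 3.0.

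**The case against.** The strongest reply is that little is lost. Table 8 prints numerators and denominators for ITT and PP, so any reader can compute a standard unadjusted interval. The clause changes no data, test or error rate. This stands, and it limits the point to pre-specification and prominence.

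Four further objections deserve weight.

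- **Much of the 38 to 54% chance of non-significance at 5% vs 2% and 4% vs 1% comes from a separate problem.** The sample-size formula has no power term. This is correct: the percentages show how often the clause would apply, not the harm it does. At full 80% power it would still apply in one trial in five with a real effect, and in about 95% or more of trials with none.
- **Exclusion at low incidence is partly automatic.** With 5 vs 5 cases the control rate is 1.6%, from which no drug could remove 3 points. The rows with 16 control cases avoid this. So, largely, does the 37% figure: only 9% of its excluding results have an observed control rate below 3%, against 99% of those behind the 69%.
- **The 3-point benchmark is tied to a control incidence of 1 to 5%.** The Protocol quotes detectable reductions of 4 points up to 8% incidence and 6 points up to 18%. Outside the 1 to 5% range the interval is still needed, but 3 points may not be the right yardstick.
- **The SAP says if, not only if.** It does not forbid an interval otherwise. But a plan that covers one case has not planned the other.

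The gap is also wider than the condition alone: even after a significant result, no scale, method or table row is specified.

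**Conclusion.** The concern holds. Nothing in either document plans an unconditional interval for the between-group difference on the primary endpoint. After a non-significant test, the planned output cannot show whether the Protocol's 3-point minimum effect has been excluded.

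At 315 per arm this situation arises in 48% of trials if the true rates are 5% and 2%, and in 95% if both are 5%. It is rare only for large relative effects, such as 14% vs 2%. These figures assume independent binomial outcomes, the SAP's test rule as written, no missing outcomes and the stated true rates. The exclusion results use the Newcombe method, and another method could differ slightly near 3 points.

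The validity of the primary test is not in question. The change should be made because it decides what a null result can say, but it is not critical.

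**What to change.** In SAP 5.1, delete the condition on statistical significance. State that for the primary endpoint, in both ITT and PP, the risk difference will be reported with a two-sided 95% confidence interval by a named method, whatever the p-value. Newcombe or Miettinen-Nurminen would both suit the low event counts. Add a row for the difference and its interval to Table 8. The same row can be added to Tables 9 to 12 for the secondary proportions.

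The cost is one sentence and one table row, with no extra data and no burden on participants.
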